4.3 Estimands

We define the following estimands for the outcomes.

Estimand E1.1: This estimand quantifies the effectiveness of the treatment assessed with the reduction of symptom severity (co-primary outcome).

Outcome of interest: Number of days needed to achieve a 50% reduction on the Acute Bronchitis Severity Score (ABSS) after peak of symptoms, assessed at max. 22 days. The peak of symptoms is defined by the highest ABSS (or the initial score if there is no peak). This is a normally distributed count outcome (3).

Population-level summary measure of outcome: adjusted* mean difference.

Participant-set of interest: FAS.

Handling of intercurrent events: All participants are included.

Handling of missing data: Missing data will be multiple imputed (see section 6.4).

* 1) Adjusted for the type of recruitment (PCP/walk-in clinic) and 2) adjusted for the following factors at baseline: type of recruitment, age, sex, level of education, smoking status, beginning of symptoms (number of days), baseline ABSS, and prescriptions for corticosteroid containing oral medication or inhalers (yes/no), including Prednisone, Symbicort, and Vannair.

Estimand E1.2: This estimand quantifies the effectiveness of the treatment assessed with the reduction of symptom severity (co-primary outcome) in the PP population.

Outcome of interest: Same as estimand 1.1.

Population-level summary measure of outcome: same as estimand 1.1.

Participant-set of interest: PP.

Handling of intercurrent events: Participants with ICE1-3 are excluded from the analysis. The data will be weighted according to inverse probability weighting for ICE 1 and 2 (see section 6.2.2).

Handling of missing data: As ICE cannot be assessed in participants who drop out or are lost to follow-up, we will not use multiple imputation. We will use inverse probability of attrition weights to account for attrition and multiple imputation for missing baseline covariates (see section 6.4).

SAP for PHYTOBRONCH	Version of SAP: 1	
Based on template: CTU_STA_TEM-11; v5.0.0	Valid from: 20.03.2025	Page 8 of 15

Estimand E2.1: This estimand quantifies the efficacy of the treatment assessed with the proportion of antibiotics use (co-primary outcome).

Outcome of interest: Use of antibiotics after the initial visit (binary).

Population-level summary measure of outcome: adjusted* risk ratio.

Participant-set of interest: FAS.

Handling of intercurrent events: All participants are included. Participants who took antibiotics at baseline will be considered as failures (having antibiotics).

Handling of missing data: Missing data will be multiple imputed (see section 6.4).

* Same adjustment as E1.1. If there are too few participants, we will use analyses adjusting separately for each covariate + type of recruitment.

Estimand E2.2: This estimand quantifies the efficacy of the treatment assessed with the proportion of antibiotics use (co-primary outcome) in the PP population.

Outcome of interest: same as estimand 2.1.

Population-level summary measure of outcome: same as estimand 2.1.

Participant-set of interest: PP.

Handling of intercurrent events: Participants with ICE1-3 are excluded from the analysis. The data will be weighted according to inverse probability weighting for ICE 1 and 2 (see section 6.2.2).

Handling of missing data: As ICE cannot be assessed in participants who drop out or are lost to follow-up, we will not use multiple imputation. We will use inverse probability of attrition weights to account for attrition and multiple imputation for missing baseline covariates (see section 6.4).

Estimand E3.1: This estimand quantifies the incidence of AEs and SAEs.

Outcome of interest: Presence of any adverse or severe adverse event (binary) during the follow-up (up to 22 days).

Population-level summary measure of outcome: adjusted^{*} hazard ratio.

Participant-set of interest: SAF.

Handling of intercurrent events: All participants are included.

Handling of missing data: No missing data, participants are censored when the study ends (at day 22) or at the day of last contact.

* 1) Adjusted for the type of recruitment (PCP/walk-in clinic) and 2) adjusted for the following factors at baseline: type of recruitment, age, sex, level of education, smoking status, beginning of symptoms (number of days), and baseline ABSS. If there are too few participants, we will use analyses adjusting separately for each covariate + type of recruitment.

Estimand E3.2: This estimand quantifies the incidence of AEs and SAEs.

Outcome of interest: same as estimand 3.1.

Population-level summary measure of outcome: same as estimand 3.1.

Participant-set of interest: SAF without ICE2.

Handling of intercurrent events: Participants with ICE2 are excluded from the analysis. The data will be weighted according to inverse probability weighting for ICE 2 (see section 6.2.2). Participants will be censored when they deviate from the treatment strategy (ICE1) and when they have a terminal event (ICE3).

Handling of missing data: No missing data, participants are censored when the study ends (at day 22) or at the day of last contact.

SAP for PHYTOBRONCH	Version of SAP: 1	
Based on template: CTU_STA_TEM-11; v5.0.0	Valid from: 20.03.2025	Page 9 of 15

Estimand E4: This estimand quantifies the proportion of PCPs who agree to participate in the study.

Outcome of interest: PCP agrees or declines to participate in the study (binary).

Population-level summary measure of outcome: Percentage.

Participant-set of interest: FAS PCPs.

Handling of intercurrent events: All PCPs are included.

Handling of missing data: No missing data (missing data are considered as refusal to participate in the study).

SAP for PHYTOBRONCH	Version of SAP: 1	
Based on template: CTU_STA_TEM-11; v5.0.0	Valid from: 20.03.2025	Page 10 of 15

5. Trial Population

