2.1 Trial design

This is a pragmatic, open-label, superiority randomized controlled trial, which takes place in ~40 PCP in practices and 5 walk-in clinics. The intervention group receives Kaloba® for 7 days and up to 21 days. The control group receives usual care, with symptomatic treatments freely chosen by the PCP (phytotherapy excluded). Usual care is not standardized between PCPs. A delayed use of antibiotics can be used in both groups. Prescription of paracetamol is allowed, as well as any routine medication pre-reviewed by the PCP and not counter-indicated.

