2.2 Randomization

Participants are randomized in a 1:1 ratio to either the intervention group or the control group, with stratification according to PCP. Randomization was performed using blocks of equal size (size=4). An independent statistician built the randomization table.

Study group allocation is done using the web-based system REDCap (hosted by the University of Fribourg), which also contains the electronic case report form (eCRF). The PCP uses the button "randomize" in REDCap to allocate each patient to a group.

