2.3 Sample size

The sample size was calculated for each of the co-primary outcomes, using a Bonferroni correction for the significance level (.05 / 2 = .025). It was replicated in Stata 18 as follows:

- Reduction of symptom severity: Using a two-sample means test with power = 80%, a two-sided significance level = 2.5%, an allocation ratio 1:1, one day of difference between groups (Δ=1), and a standard deviation of 3 days assumed to be the same in both groups (1), we needed n=346 (173 in each group).
- Antibiotics use: Using a two-sample proportions test (Pearson's chi-squared test) with power = 80%, a two-sided significance level = 2.5%, an allocation ratio 1:1, a proportion of 60% in the control group and 45% in the intervention group (Δ =15) (2), we needed n=420 (210 in each group).

The largest sample size estimation was selected: n=420. As this approach is rather conservative (e.g., it does not consider the fact that the co-primary outcomes may be correlated), we did not account for potential drop-out in the sample size calculation.

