5.3 Baseline patient characteristics

Baseline parameters will be presented as means and standard deviations for continuous variables, or percentages and n for categorical variables.

The baseline table will include standardized mean/proportion differences to have an overview of the balance between groups, but no p-values or confidence intervals.

Relevant baseline covariates include:

- Socio-demographics: sex, age, level of education (primary, secondary, or university)
- Risk factors: smoking (yes/no), comorbidities (hypertension, diabetes, cardiovascular disease, cancer, obesity),
- Illness-related variables: number of days since the beginning of symptoms, baseline ABSS, medications already used (cough suppressant, expectorant, anti-inflammatory, febrifuge, other)
- Medical background: COVID-19 vaccination.

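### The corticosteroid-prescription covariate in both co-primary models is not limited to prescriptions that predate randomisation, so it may include part of usual care

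*Combined protocol and SAP*

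**What the plan says.** SAP 4.3 gives E1.1 two adjustment sets. The first contains only type of recruitment. The second adds demographic and illness factors described as baseline, among them baseline ABSS, and ends with "prescriptions for corticosteroid containing oral medication or inhalers (yes/no), including Prednisone, Symbicort, and Vannair". E2.1 uses the same adjustment, with a fallback that enters covariates one at a time if there are too few participants. The per-protocol estimands E1.2 and E2.2 take over the same summary measures. SAP 6.2.1 bases the primary analysis on the adjusted model with the predefined covariates, so the corticosteroid item is in both co-primary models.

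On the comparator, SAP 2.1 describes usual care "with symptomatic treatments freely chosen by the PCP (phytotherapy excluded"), not standardised between physicians. Routine medication that the physician has reviewed is also allowed. Under SAP 2.2 the physician triggers the allocation in REDCap, and under 2.8 nobody is blinded. SAP 5.2 requires a first consultation for the episode and excludes asthma and COPD as causes.

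For treatment before the visit, the baseline list in SAP 5.3 uses different words: "medications already used (cough suppressant, expectorant, anti-inflammatory, febrifuge, other".

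**The concern.** A covariate fixed before randomisation can be adjusted for safely. A treatment chosen after allocation cannot, because it may depend on the arm. Here the variable is a prescription, the prescriber knows the allocation, and the prescriber's free choice of treatment is the control condition. Participants are at their first consultation for the episode, so a corticosteroid prescribed for it would most plausibly be written at the inclusion visit. That visit can contain both the randomisation and the choice of usual care, and the word baseline does not say on which side of the allocation the prescription falls.

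If prescriptions written after allocation are counted, the model holds part of the comparator constant. The coefficient for arm is then no longer the effect of Kaloba against usual care that SAP 1.2 and 2.4 set out to estimate. Two mechanisms pull in opposite directions. If corticosteroids help and are given more often in the control arm, their benefit is taken out of the control arm and Kaloba looks better than it is. If they go to sicker patients, the prescribed patients in the two arms are no longer comparable, and Kaloba can look worse than it is.

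**Working it through.** **1. The plan's own figures (SAP 2.3).** Inputs: 80% power, two-sided 2.5% per co-primary, 1:1 allocation.

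- Symptoms: "one day of difference between groups (Δ=1), and a standard deviation of 3 days". Normal approximation: n per arm = 2 × (2.2414 + 0.8416)² × 3² / 1² = 171.1, so 172. The t-based version gives 173 per arm, 346 in total, as stated.
- Antibiotics: "a proportion of 60% in the control group and 45% in the intervention group". n per arm = [2.2414 × √(2 × 0.525 × 0.475) + 0.8416 × √(0.60 × 0.40 + 0.45 × 0.55)]² / 0.15² = 209.4, so 210, and 420 in total, as stated.

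With 210 per arm, power is 0.88 for the symptom outcome and 0.80 for antibiotics. The sample size is not in question. It supplies the scale: a planned difference of 1 day.

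**2. Assumptions.** The documents give no corticosteroid prescribing rate by arm and no effect. All values below are therefore assumed, and all prescriptions are taken to be written after allocation. Let pK and pC be the proportions prescribed in the Kaloba and usual-care arms, and g the corticosteroid effect in days (negative means shorter).

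**3. Corticosteroids act, and prescribing is unrelated to severity.** In a linear model:

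adjusted effect = total effect − g × (pK − pC)

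With g = −1 and pK = 5%:

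| pC | g × (pK − pC) | Shift in the arm coefficient |
|---|---|---|
| 5% (equal) | 0 | 0 |
| 10% | −1 × (−0.05) = 0.05 | −0.05 day |
| 20% | −1 × (−0.15) = 0.15 | −0.15 day |
| 40% | −1 × (−0.35) = 0.35 | −0.35 day |

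A negative shift favours Kaloba. At 20–40%, a total effect of −0.85 to −0.65 day would be reported as about −1.00.

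**4. Corticosteroids do nothing, but sicker patients receive them.** Assume severity is worth 1 day per SD and raises the odds of a prescription by a factor of 2 per SD. Then:

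adjusted effect = total effect − 1 × d × (pK − pC)

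Here d is the within-arm difference in severity, in SD, between prescribed and unprescribed patients that the model has not already removed. It was found by numerical integration over a normal severity distribution. With a total effect of −1.00 and pK = 5%:

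| pC | Severity not otherwise in the model | Baseline ABSS captures half of its variance |
|---|---|---|
| 10% | d = 0.66: −0.97 | d = 0.34: −0.98 |
| 20% | d = 0.65: −1 + 0.65 × 0.15 = −0.90 | d = 0.33: −0.95 |
| 40% | d = 0.63: −1 + 0.63 × 0.35 = −0.78 | d = 0.33: −0.89 |

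If baseline ABSS captured all of the relevant severity, the shift would be zero. With a steeper link (log-odds slope 1 per SD) and severity not in the model, the results at 10%, 20% and 30% versus 5% are −0.96, −0.87 and −0.78.

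**5. Effect on power.** The standard error is 3 × √(2/210) = 0.293. At −1.00, power is Φ(1.00/0.293 − 2.241) = 0.88. At −0.78 it is Φ(0.78/0.293 − 2.241) = 0.66.

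**6. Both mechanisms together.** They can cancel. At 20% versus 5% with g = −1 and slope 1, the adjusted effect is −1.02 against a total of −1.00.

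No shift was calculated for the antibiotics risk ratio. The same argument applies to it, but its size would need further assumptions.

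**The case against.** The strongest reply is that the SAP already labels the list as baseline, and that every other item in it (age, sex, education, smoking, symptom duration, baseline ABSS) is plainly fixed before treatment. The natural reading is that the corticosteroid item is too, and then the adjustment is harmless. Routine medication is allowed in both arms, and excluding asthma and COPD as causes of the illness does not rule out people who already hold an inhaler or oral prescription. This stands as the more charitable reading. It does not settle the matter, because no section ties the prescription to a time before allocation, and the wording differs from that used for prior medication in 5.3.

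A reader might infer that the variable must be post-randomisation because it is not named in the 5.3 list and is missing from the E3.1 adjustment set, the imputation auxiliaries and the weighting covariates. That inference is weak. E3.1 concerns a different outcome, auxiliary lists need not repeat every covariate, the ICE1 weights also omit smoking, and the categories in 5.3 for anti-inflammatory and other medication could contain corticosteroids.

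Two safeguards also deserve credit. The first adjustment set omits the covariate, although 6.2.1 makes the model with predefined covariates primary. Baseline ABSS is in the same model and would absorb some confounding by severity, roughly halving it if it captures half of the severity variance.

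**Conclusion.** The point holds as an unresolved timing definition that could bias both co-primary estimates. It is not a demonstrated bias. A reader might go further and conclude that the primary analysis does condition on a post-randomisation treatment, or that it will overstate Kaloba by about a third of a day. The documents support neither: they do not name corticosteroids as usual care, do not say prescribing differs by arm, and give no rates.

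Bias needs two things together: prescriptions after allocation must be counted, and prescribing must differ between arms. The calculated sizes are for the symptom outcome. The shift is nil with equal prescribing and about 0.02 to 0.05 day at 10% versus 5%. At 20–40% versus 5% it is 0.15 to 0.35 day in favour of Kaloba with a one-day corticosteroid effect, or about 0.05 to 0.22 day against Kaloba if there is no effect but sicker patients are prescribed it. The last range assumes an odds ratio of 2 per SD, one day per SD of severity, and baseline ABSS capturing between none and half of the severity variance. In an open-label trial, equal prescribing cannot be taken for granted, so a change this cheap is worth making.

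**What to change.** In E1.1 and E2.1, define the covariate as corticosteroid-containing medication prescribed or in use before randomisation, and check it against the date or time of allocation. If the eCRF cannot separate the timing, leave the item out of the primary models, report corticosteroid prescriptions by arm, and show the model that includes it only as a labelled sensitivity analysis. Make the change before the data are analysed.

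The cost is a change of SAP wording and the possible loss of one prognostic covariate. The sample size stays at 420. The point concerns the analysis only and takes no view on whether corticosteroids should be prescribed.

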5.1 Screening data

Not available.

5.2 Eligibility

The target study participants are outpatients with acute bronchitis (with or without COVID-19).

Inclusion criteria are:

- 1. At least 18 years old
- 2. Consulting for the first time as part of this bronchial episode
- 3. Consulting for:
 - a. Acute cough (≤ 8 days) as the main symptom
 - b. Illness (≤ 8 days) in which cough is not the main symptom, but the PCP believes that acute bronchitis is the most likely diagnosis

Exclusion criteria are:

- 1. Infection requiring antibiotics
- 2. Pneumonia
- 3. Non-infectious causes (COPD, asthma, pulmonary embolism, heart failure, gastro-esophageal reflux, allergy)
- 4. Incapacity of judgment (dementia, psychosis or severe depression)
- 5. Important risk of bleeding (severe thrombocytopenia and anticoagulant intake)
- 6. Inability to complete the diary
- 7. Pregnancy or breastfeeding
- 8. Immunological deficiencies
- 9. Severe hepatic disease
- 10. Known hypersensitivity to Pelargonium sidoides extract or excipients of the trial medication
- 11. Currently taking Kaloba® or Umckaloabo® for this current episode of acute bronchitis
- 12. Taking anticoagulants, immunosuppressants, chemotherapy or immunotherapy

A CONSORT patient flow diagram will be drawn.

5.3 Baseline patient characteristics

Baseline parameters will be presented as means and standard deviations for continuous variables, or percentages and n for categorical variables.

The baseline table will include standardized mean/proportion differences to have an overview of the balance between groups, but no p-values or confidence intervals.

Relevant baseline covariates include:

- Socio-demographics: sex, age, level of education (primary, secondary, or university)
- Risk factors: smoking (yes/no), comorbidities (hypertension, diabetes, cardiovascular disease, cancer, obesity),
- Illness-related variables: number of days since the beginning of symptoms, baseline ABSS, medications already used (cough suppressant, expectorant, anti-inflammatory, febrifuge, other)
- Medical background: COVID-19 vaccination.

5.4 Adherence and protocol deviations

Protocol violations will be summarized by percentages and n in each group.

SAP for PHYTOBRONCH	Version of SAP: 1	
Based on template: CTU_STA_TEM-11; v5.0.0	Valid from: 20.03.2025	Page 11 of 15

5.5 Withdrawal/follow-up

Withdrawal from the study and lost-to-follow-up will be summarized by percentage and n in each group.

6. Analysis

6.1 Outcome definitions

Reduction of symptom severity. The first co-primary endpoint uses the patient-reported outcome Acute Bronchitis Severity Score (ABSS), which quantifies the severity of 5 symptoms related to acute bronchitis for the previous 24 hours. It is assessed on a scale from 0 to 4, with the sum score ranging between 0 and 20 (see Table 1) (3). Participants will complete the ABSS daily on an online diary, until symptom resolution and up to 21 days. If the participant does not answer, the ABSS will be evaluated in phone interviews (days 4, 8, and 22).

Symptom	0	1	2	3	4
Overall severity of illness	Very mild	Mild	Moderate	Serious	Very serious
Day cough	1-2 times/day	3-5 times/day	6-10 times/day	11-20 times/day	>20 times/day
Night cough	1-2 times/night	3-5 times/night	6-10 times/night	11-20 times/night	>20 times/night
Limit daily activity	None	Mild	Moderate	Severe	Very severe
Subjective fever	None	Mild	Moderate	Severe	Very severe

Table 1. Acute Bronchitis Severity Score (ABSS)

The first co-primary is the number of days needed to achieve a 50% reduction in the ABSS after peak of symptoms (1). The peak of symptoms is defined as the highest ABSS observed during the study.

The procedure to calculate the first co-primary endpoint is the following:

- Calculate daily ABSS (sum score of the 5 symptoms)
- Calculate the peak (max. ABSS observed)
- Calculate daily percentage change in the ABSS after the peak
- Calculate which day corresponds to a 50% decrease
- Calculate the number of days between the peak and the 50% decrease

If there is no peak, the first day will be used as the peak. If the 50% decrease is not reached, we will set the number of days to the maximum (22 days). Imputation will be used for missing values on daily ABSS (see section 6.4). We will run a sensitivity analysis computing the primary outcome and using multiple imputation on the primary outcome.

Antibiotics use. The second co-primary endpoint is the proportion of participants who take antibiotics after the initial visit (\geq day 2). It is defined as 0=no antibiotics during the same illness episode and 1=antibiotics use during the same illness period. Antibiotics use is assessed daily in the diary (day 1 to 21) until symptom resolution and at the three phone calls at day 4, 8, and 22.

AEs and SAEs. The first secondary endpoint will include AEs, predefined according to the dictionary MedDRA and SAEs, defined according to the HRA. Assessments of severity (5 categories, from grade 0 to 5) and causality (5 categories, from "not related" to "definitely related") will also be evaluated. We will compute a single endpoint with 0=no AE or SAE during the study and 1=at least one AE or SAE during the study period. We will also create separate endpoints for AEs and SAEs and types of AEs/AEs. The date of the (S)AEs will also be recorded, to capture the time until (S)AE.

SAP for PHYTOBRONCH	Version of SAP: 1	
Based on template: CTU_STA_TEM-11; v5.0.0	Valid from: 20.03.2025	Page 12 of 15

PCP agreement to participate in the study. The second secondary endpoint will assess whether the PCP agrees to participate in the study. Participation will be defined as signing the agreement and enrolling participants. Non-participation will be defined as refusing or signing but not enrolling participants.

